# **1.2.** Brief description of methodology, including design, population, and variables of interest

This will be a prospective randomized controlled trial of Auburn University (AU) employees or an adult sponsored dependent of an active employee (<18 years old) who was insured by the AU Health and Pharmacy Insurance plan during 2015 and enrolled in the Health Insurance plan for 2016 and/or 2017. Eligible patients are 1) those completing their "Healthy Tigers" biometric screening between 01/01/2015-5/31/16, 2) who had a BMI  $\geq$  30 and two or more of the following CVD risk factors: male, age 55-80; female, age 60-80; current smoker; family history of premature coronary heart disease; received a red or yellow zone reading for their blood pressure, blood glucose, total cholesterol; those with a diagnosis of hypertension, pre-diabetes, or hypercholsterolemia; a patient of the AU Employee Pharmacy enrolled in the TigerMeds program with an existing diagnosis of hypertension, pre-diabetes, or hypercholesterolemia. Patients will be randomized into two groups: the AHA vs MD. The study will consist of a 12-week nutrition education program that includes dietary nutrition education sessions (both groups) and extra virgin olive oil and mixed nut supplementation (MD group). We will assess program impact by comparing baseline characteristics including body mass index, blood pressure, blood glucose, and total cholesterol, etc., and reassessing the same measures at week 6 and week 12 of the study.

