#### 2. Purpose

#### 2.1. Purpose of this project including research questions and/or aims

The primary objective of this pilot study is to assess the efficacy of a MD intervention (education + EVOO and mixed nut supplementation) versus that of an AHA nutrition intervention (education) on serum blood lipid levels as markers for cardiovascular disease risk. As secondary outcomes we will assess insulin resistance, serum metabolic factors, blood pressure, body mass index, and waist circumference.

Research Question: In the Southeastern United States, is the dietary pattern of the American Heart Association or a Mediterranean style diet more effective in the reduction of CVD risk factors.

Aim 1: To assess whether or not patients have improvements in their CVD risk factors by the end of the 12-week program.

Aim 2: To assess which dietary intervention is most effective in the reduction of CVD risk factors at the end of the 12-week program.

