  - 5. Individuals who anticipate absence or travel throughout the study that would interfere with their ability to complete the analysis at the mid-point and end of challenge.
  - 6. Patients with a peanut, tree nut, or olive oil food allergy or intolerance.
  - 7. Patients who are unable or unwilling to travel to Auburn University main campus for live health and wellness challenge events, individual assessments, personal appointments, and pre- and post- data collection
  - 8. Individuals who have NOT been stabilized on medication to treat or manage high blood pressure, high cholesterol, dyslpidiemia, or pre-diabetes for at least 12 weeks prior to the study.
  - 9. Patients who do not have access to the internet and therefore unable to complete the education portion of the study
  - 10. Individuals who have a pacemaker
  - 11. Patients who decline participation during informed consent

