### 4.2. Research design and methods

- Participants will be seen at the Auburn University Pharmaceutical Care Clinic (AUPCC) for their initial "Healthy Tigers" Healthy Hearts Program consenting visit. The assessment will include a health and wellness interview, International Physical Activity Questionnaire, Diet History Questionnaire II, a Mediterranean diet knowledge/adherence survey, and the completion of the eligibility form. During this visit, the letter of consent will be given to and discussed with the participant. If the participant chooses to participate, their signature will be obtained on the consent form.
- 2) a) Participants will then return to the Auburn University Pharmaceutical Care Clinic (AUPCC) for their baseline "Healthy Tigers" Healthy Hearts Program visit. Pharmacists and pharmacy residents, employed by the AUPCC will obtain the following: height measurement (inches), weight measurement (pounds), Calculated BMI (kg/m2) measurement of body composition (using bioelectrical impedance analysis) (% body fat, pounds of fat, pounds of lean mass, pounds of total body water), waist measurement (inches), hip measurement (inches), Waist to Hip Ratio, Waist to Height Ratio, Systolic blood pressure (mmHg), Diastolic blood pressure (mmHg), resting pulse (bpm), fasting blood glucose (mg/dL), fasting total cholesterol (mg/dL), fasting LDL-cholesterol (mg/dL), fasting HDL-cholesterol (mg/dL), fasting Triglycerides (mg/dL), total Cholesterol to HDL ratio, Atherosclerotic cardiovascular disease risk (ASCVD) Score (%), fasting insulin mI/L, fasting leptin ng/mL, IL-6 (pg/mL), tumor necrosis factor-α (pg/mL), urinary tyrosol and hydroxytyrosol. These measurements will be repeated at week 6 and week 12 of the trial.
  - b) At this baseline appointment, the patient will also receive a baseline medication therapy management (MTM) assessment by a pharmacist in order to identify any potential or actual drug-related problem (DRPs), and to monitor for efficacy and safety of all medications, make recommendations for vitamins, minerals, and supplements, and provide preventative care recommendations (such as immunizations, osteoporosis screenings, colonoscopy, mammograms, and other recommended medical screenings that are recommended for the patient's age, gender, and concomitant disease states and medications).

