# **Total Participant Involvement Time**

#### 340 minutes

- 5) STUDY REQUIREMENTS
  - a) The participants will be asked to follow a dietary pattern that is associated with their assigned intervention group. The Mediterranean Diet (MD) group will be given supplements of extra virgin olive oil (EVOO) and mixed nuts. Participants in this group will be asked use these supplements as a part of their daily intake. A total of 6 L of EVOO and 6 pounds of mixed nuts (3 pounds raw walnuts and 3 pounds raw almonds) will be administered throughout the study. Participants in the MD group will be given 3 L of EVOO and 3 pounds of mixed nuts at the baseline appointment asked to return unused portions of at their 6-week appointment. At that time they will be given a new supplementation of 3 L or EVOO and 3 pounds of mixed nuts. Participants will be given the same instructions for use and asked to return unused portions at the end of the study (week 12).
  - b) The participants might have follow-up appointments scheduled with the pharmacist within the AUPCC depending on the patient's personal care plan that is developed at baseline. For instance, if a patient has potential or actual drug-related problems that are identified on their baseline MTM appointment, then the pharmacist will schedule follow-up appointments that are appropriate for the problem and the plan of care that is developed to address these problems. This will be done consistently between all patients in the study, regardless of the randomization (the pharmacist and the will be blinded concerning which group the patient is randomized to concerning dietary intervention).
  - c) Narrated nutrition education presentations will be developed by a registered dietitians, dietetic interns, graduate students, and faculty. These presentations will be loaded on the "Healthy Hearts Program" website. The participants will be asked one presentation weekly for the first 6 weeks of the study and then one additional education module at week 9. A post-presentation assessments will load after the presentation is completed, and completion of the assessment will be used as verification that the participant watched the presentation.
  - d) The participant will complete the following at baseline, week-6 and week 12 of the study: Diet History Questionnaire II, International Physical Activity Questionnaire, and a Mediterranean diet knowledge and adherence questionnaire.

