  - e) For patients with a diagnosis of Hypertension or an elevated blood pressure reading during a "Healthy Tigers" screening that is in the yellow or red zone, home blood pressure monitoring might be integrated into the medication therapy management plan of care.

- f) For patients with a diagnosis of pre-diabetes, or who have an elevated blood glucose reading during a "Healthy Tigers" screening that is in the yellow or red zones, home blood glucose monitoring might be integrated into the medication therapy management plan of care.
- g) All participants will be asked to return to the AUPCC at weeks 6 and 12 for a repeat "Healthy Tigers" analysis and MTM consultation.

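### Sections 1.2 and 4.5 judge programme impact by change from baseline, but with two active diets and medication management for everyone, that change cannot be credited to either diet programme

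*Combined protocol and SAP*

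**What the plan says.** Section 2.1 gives Aim 1 as "To assess whether or not patients have improvements in their CVD risk factors by the end of the 12-week program". It names no comparator, no test and no cause. Aim 2 and the primary objective in the same section compare the two diets.

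Section 1.2 links change over time to the programme: "We will assess program impact by comparing baseline characteristics including body mass index, blood pressure, blood glucose, and total cholesterol", with the same measures taken again at weeks 6 and 12. It describes the programme as nutrition education for both groups, plus olive oil and nuts for the MD group. MTM is not part of that description. On the arms it says "Patients will be randomized into two groups: the AHA vs MD".

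Section 4.5 compares the outcome variables at baseline with their values at week 6 and week 12, and assigns Student's t test to continuous data. It does not say whether the test is paired or two-sample. The only comparison between the two groups that it spells out concerns baseline demographics.

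Section 4.2 adds care outside the diet programme:
- At the baseline visit, "the patient will also receive a baseline medication therapy management (MTM) assessment by a pharmacist" (items 2b and 3b).
- All participants have a further MTM consultation at weeks 6 and 12 (item 5g).
- Some may have extra pharmacist follow-up for drug-related problems. Of this the plan says "This will be done consistently between all patients in the study, regardless of the randomization" (item 5b).
- Some may have home blood pressure or glucose monitoring (items 5e and 5f).

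In section 3.1, exclusion 8 covers "Individuals who have NOT been stabilized on medication to treat or manage high blood pressure, high cholesterol" and related conditions, for at least 12 weeks before the study.

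**The concern.** Under section 1.2, a fall in cholesterol, blood pressure or glucose from baseline to week 12 would count as impact of the nutrition programme. The design has no usual-care or MTM-only arm to show what would have happened without a diet programme. Pharmacist review of all medications, with recommendations on supplements, can act on the same risk factors, and no provision holds medication fixed after entry. Time trends can also contribute. So can regression to the mean, since some participants qualify on raised screening values.

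At stake is the conclusion drawn from Aim 1. A pre-post improvement could be presented as evidence that one or both diet programmes work, when the data cannot separate diet from the rest of the package.

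**Working it through.** The documents give no sample size, significance level, effect size or SD, so there is no planned figure to reproduce. The check is a reading of the contrasts, followed by an illustration on assumed inputs.

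**1. What each contrast estimates.** Let d_MD and d_AHA be the effects of the two diet programmes on a risk factor by week 12. Let s be the shift from everything else: MTM, time and regression to the mean. Section 4.2 plans MTM irrespective of arm, so s is taken as common to both.

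- Change in the MD arm = d_MD + s
- Change in the AHA arm = d_AHA + s
- Pooled change, with a fraction p in MD = p × d_MD + (1 − p) × d_AHA + s
- Between-arm difference = (d_MD + s) − (d_AHA + s) = d_MD − d_AHA

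The shift s stays in every within-arm or pooled change and cancels in the randomised difference. With d_MD = d_AHA = 0, the pre-post contrast still estimates s, while the between-arm contrast estimates 0.

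**2. Do the documents give reason to expect s to differ from zero?**

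- MTM is planned for all participants at three visits, with conditional follow-up and home monitoring (section 4.2).
- Medication stability applies only before entry (section 3.1, exclusion 8). No section adjusts for later changes.
- Section 4.5 collects the number of drug-related problems at the start and end of the study but states no analytic use for it.
- Entry can rest on yellow- or red-zone screening values (section 3.1), which allows regression to the mean. The separate baseline visit may remove part of it.

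The direction and size of s cannot be worked out from the documents.

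**3. Illustration (n and s both assumed).** Take a two-sided 5% paired t test on n participants, no diet effect, and s in SDs of the change score. The noncentrality is s × √n; for s = 0.3 it is 0.3 × √20 = 1.34 and 0.3 × √100 = 3.00. Rejection probabilities from the noncentral t distribution:

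| n | s = 0.1 | s = 0.2 | s = 0.3 | s = 0.5 |
|---|---|---|---|---|
| 20 | 7% | 14% | 25% | 57% |
| 40 | 10% | 24% | 46% | 87% |
| 60 | 12% | 33% | 63% | 97% |
| 100 | 17% | 51% | 84% | >99% |

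A between-arm test at the same level rejects 5% of the time for every s, because s cancels.

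These are probabilities of detecting a change that did occur. They are not false-positive rates for the literal question in Aim 1. The error arises when the change is then attributed to diet.

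**The case against.** The strongest reply is that Aim 1 claims nothing causal. It asks whether patients improve, and that can be answered descriptively without a control arm. This stands. The difficulty comes from section 1.2, which calls the comparison programme impact, and section 4.5, which gives that comparison a significance test.

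A second reply is that section 1.2 is ambiguous. The sentence follows the description of randomisation and does not say that arms are pooled or that the contrast is only within arm, and section 4.5 leaves the form of the t test open. That is fair, but no sentence in either section defines a between-arm comparison of outcomes, so the ambiguity itself needs removing.

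A third reply is that the efficacy question is randomised, pharmacist follow-up is to be consistent across arms, and section 4.2 (item 5b) says the pharmacist is blinded to diet group. This also stands. A reader might infer that MTM undermines the whole trial; the documents do not support that. As planned, MTM does not bias the MD versus AHA contrast.

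Two further inferences go too far. Section 3.2 says only that people at a weigh-in programme will receive a flyer; it does not show that any were enrolled from there. The 12 weeks of stable medication before entry is also a partial safeguard, since it reduces drug effects still evolving at baseline, although it does not govern what MTM changes afterwards.

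**Conclusion.** The point holds for within-arm and pooled change. Such change describes diet education plus MTM, together with time trends and possible regression to the mean, and cannot be credited to either diet programme. Sections 1.2 and 4.5, followed as written, would credit it to the nutrition programme.

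The primary objective and Aim 2 are not affected, provided MTM is delivered equally in both arms as planned. Aim 1 itself can stand as description.

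The size cannot be stated from the documents. The range of about 25% (n = 20) to 84% (n = 100) for a 0.3 SD shift shows only how readily a pre-post test would register a non-diet change. The correction is one of wording and analysis definition; it does not call for a redesign.

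**What to change.** - **Sections 1.2 and 4.5:** base any claim of programme or diet effect on the randomised MD versus AHA difference at week 12, adjusted for the baseline value of the outcome.
- **Aim 1 (section 2.1) and section 4.5:** label Aim 1 descriptive. Report mean change with a 95% confidence interval by arm at weeks 6 and 12, interpreted as change under diet education plus MTM, with no causal claim.

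A ban on within-arm tests is not needed; what matters is that no effect claim rests on them. Reporting the drug-related problem counts by arm beside the changes would help readers, but without a non-diet arm it cannot isolate the effect of either diet programme.

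The cost is a few sentences. The measurements are already planned, and no visits or participants are added. The downside is that the plan gives up a favourable within-group claim, and the between-arm difference measures only how the MD package compares with AHA education, not the effect of either against no programme.

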#### 4.5. Data analysis

Descriptive statistics will be conducted and presented for the population. Baseline demographics will be compared between the 2 groups and compared using the appropriate test for each data point. Continuous variables will be compared using student t-tests, categorical variables will be compared using chi-square tests, etc. Age will be collected as a continuous variable (years). Ethnicity will be collected as a categorical variable (Caucasian, Asian, African-American, Hispanic, Other, Not Reported). Level of education will be collected as a categorical variable (high school, some college, college degree, graduate degree, professional degree, etc.), smoking status will be collected as a categorical variable (never smoked, past smoker, current smoker), baseline ASCVD risk score (collected as a continuous variable), obesity (dichotomous), HTN (dichotomous), hypercholesterolemia (dichotomous), Number of patients with 1 disease state (continuous), number of patients with 2 disease states (continuous), number of patients with 4 disease states (continuous), number of yellow values (continuous), number of red zone values (continuous).

Baseline data on change in baseline body weight (%), change in total body weight (kg), calculated BMI (kg/m2) measurement of body composition (using bioelectrical impedance analysis) (% body fat, pounds of fat, pounds of lean mass, pounds of total body water), waist measurement (inches), hip measurement (inches), Waist to Hip Ratio, Waist to Height Ratio, Systolic blood pressure (mmHg), Diastolic blood pressure (mmHg), resting pulse (bpm), fasting blood glucose (mg/dL), fasting total cholesterol (mg/dL), fasting LDL-cholesterol (mg/dL), fasting HDL-cholesterol (mg/dL), fasting Triglycerides (mg/dL), total Cholesterol to HDL ratio, and ASCVD Score (%)) fasting insulin mI/L, fasting leptin ng/mL, IL-6 (pg/mL), tumor necrosis factor-α (pg/mL), urinary tyrosol and hydroxytyrosol, will be compared to data at week-6 and the end of the 12 weeks

- Student's T test will be used to compare the continuous data collected in the study
- Chi Square test will be used to compare the categorical data collected in the study

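### The research question and Aim 2 choose the better diet on undefined CVD risk factors, so a chance week 12 result on a secondary outcome can answer them even if the lipid result is null

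*Combined protocol and SAP*

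**What the plan says.** Section 2.1 contains three statements about what the trial will decide.

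- The primary objective compares the Mediterranean diet (MD) with the American Heart Association (AHA) intervention "on serum blood lipid levels as markers for cardiovascular disease risk". No single lipid is named.
- The secondary outcomes are five domains, without an order: "As secondary outcomes we will assess insulin resistance, serum metabolic factors, blood pressure, body mass index, and waist circumference".
- The research question asks whether the AHA pattern or a "Mediterranean style diet more effective in the reduction of CVD risk factors", and gives no time point. Aim 2 reads "To assess which dietary intervention is most effective in the reduction of CVD risk factors at the end of the 12-week program".

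CVD risk factors are not defined as an endpoint. The protocol does use the term elsewhere. The eligibility lists in sections 1.2 and 3.1 place blood pressure and blood glucose under it beside total cholesterol. Section 1.2 also says that programme impact will be judged on an open list of measures: "body mass index, blood pressure, blood glucose, and total cholesterol, etc., and reassessing the same measures at week 6 and week 12 of the study".

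Section 4.5 lists 27 continuous measures, to be compared between baseline, week 6 and week 12. Five are lipid measures: "fasting total cholesterol (mg/dL), fasting LDL-cholesterol (mg/dL), fasting HDL-cholesterol (mg/dL), fasting Triglycerides (mg/dL), total Cholesterol to HDL ratio". The test is given in one line: "Student's T test will be used to compare the continuous data collected in the study". The section states no significance level, no order of testing, no exploratory label and no rule for results that disagree.

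**The concern.** The sentences that state the trial's conclusion are wider than its primary objective. By the protocol's own use of the term, a between-arm difference in blood pressure or fasting glucose at week 12 is a difference in a CVD risk factor, so it answers Aim 2. It does so even if the lipids show no difference or favour the other diet. Two secondary outcomes could also favour different diets, and nothing says which one decides.

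At stake is the error rate of the headline claim. Section 2.2 plans a dissertation, a publication and a conference abstract. A report that one diet is more effective could rest on a chance finding among outcomes that section 2.1 itself calls secondary. Choosing one primary lipid would not cure this alone, because the research question and Aim 2 would still be open to any risk factor.

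**Working it through.** The plan gives no alpha, power or sample size, so it has no figure to reproduce. The check counts the outcomes that could decide Aim 2 and finds the chance of at least one false positive among them.

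**Inputs from the documents**

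- Time point: week 12 only, because Aim 2 fixes the end of the programme.
- Section 4.5 list: 27 measures. Removing the 5 lipid measures leaves 22. Removing the two urinary olive-oil markers (tyrosol, hydroxytyrosol) leaves 20: percent and kg weight change, BMI, four body-composition measures, waist, hip, two waist ratios, systolic and diastolic pressure, pulse, glucose, ASCVD score, insulin, leptin, IL-6 and TNF-α.
- Secondary domains in section 2.1: 5, taken here as one outcome each. This is approximate, since some domains hold more than one measure.
- Non-lipid measures that section 3.1 names as CVD risk factors and section 4.5 lists as outcomes: 3 (systolic pressure, diastolic pressure, fasting glucose).

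**Assumptions**

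- Each outcome has a two-sided between-arm test at 0.05. The level is assumed, and the between-arm test is implied by Aim 2.
- There is no true difference on any outcome.
- Test statistics are normal with one common correlation ρ, varied from 0 to 0.7. The documents give no correlations.

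**Formula**

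For m independent tests, P(at least one false positive) = 1 − 0.95^m:

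- m = 3: 1 − 0.8574 = 0.143
- m = 5: 1 − 0.7738 = 0.226
- m = 20: 1 − 0.3585 = 0.642

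For common correlation ρ, P = 1 − ∫ φ(u) · [Φ((1.96 − √ρ·u)/√(1−ρ)) − Φ((−1.96 − √ρ·u)/√(1−ρ))]^m du. Numerical integration gives:

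| Outcomes at week 12 | ρ = 0 | ρ = 0.3 | ρ = 0.5 | ρ = 0.7 |
|---|---|---|---|---|
| 3 (systolic, diastolic, glucose) | 14% | 14% | 13% | 11% |
| 5 (one per secondary domain) | 23% | 21% | 18% | 15% |
| 20 (all listed non-lipid measures) | 64% | 54% | 42% | 29% |

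Simulation of the 5- and 20-outcome cases agrees to within about half a percentage point. At ρ = 0.9 the three rows fall to about 8%, 10% and 16%, still above 5%.

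The expected number of false positives does not depend on ρ: 5 × 0.05 = 0.25 for five outcomes, and 20 × 0.05 = 1 for twenty.

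**Check on the remedy**

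Tying Aim 2 to lipids in general would not control the error either. Five lipid measures give 1 − 0.95^5 = 22.6% if independent, and about 10% to 21% for ρ from 0.9 to 0.3. One named lipid at week 12, tested once at 0.05, gives 5%.

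**The case against.** The strongest reply is that section 2.1 already has a hierarchy. Lipids are primary and five domains are secondary, so Aim 2 can be read as restating the primary objective in general terms. Nowhere does the protocol say that one significant secondary outcome decides which diet is better. This is a fair reading, but the text does not require it. The protocol's own use of CVD risk factors includes blood pressure and glucose, and neither section 2.1 nor 4.5 says which outcome governs. What is missing is narrower than a hierarchy: an order within the secondary domains, a status for the other listed measures, and a rule for mixed results.

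Three stronger readings are tempting, and the documents do not support them.

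- **That week 6 results can also answer Aim 2, which would double the number of tests.** Aim 2 is limited to the end of the 12 weeks. Week 6 enters through section 1.2 and the comparisons with baseline in section 4.5. The research question is undated, but nothing makes week 6 a deciding time.
- **That all 20 non-lipid measures are rival endpoints for Aim 2.** The list includes pulse, lean mass and total body water, which the protocol never calls CVD risk factors. It also includes near-restatements of one change, such as weight change in percent and in kg, or waist and waist-to-height ratio. A single common correlation describes that structure poorly. The 20-outcome row is an upper case.
- **That the plan commits to testing each outcome at full alpha.** It states no alpha, and the only two-group comparison that section 4.5 spells out is of baseline demographics.

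The study also calls itself a pilot. This is a good reason not to demand formal alpha adjustment. It does not make any comparison exploratory, because section 2.1 says that the pilot will assess efficacy of one intervention against the other.

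**Conclusion.** The concern holds for week 12. The research question and Aim 2 rest on an undefined endpoint wider than the lipid objective, and the analysis section has no rule to close the gap. The chance of at least one false finding that one diet is more effective is about 18% for five secondary outcomes (15% to 23% for correlation 0.7 to 0). It is 11% to 14% for the three non-lipid measures that the protocol most clearly treats as risk factors. The 29% to 64% for all 20 listed measures is a ceiling and should not be quoted as the expected size.

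These figures rest on an assumed two-sided 0.05 per between-arm test, no true difference, and a common correlation that the documents do not supply. The conclusion does not depend on the exact values, since even the three-outcome case is more than twice 5% across that range. The change should be made, but the study can run without it; the harm lies in how results would be claimed.

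**What to change.** In section 2.1, name one lipid measure as primary, for example fasting LDL-cholesterol. Reword the research question and Aim 2 so that the conclusion on which diet is more effective rests only on the MD versus AHA contrast in that measure at week 12.

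In section 4.5, state that contrast as the primary test, with its significance level. Label the other lipids, all non-lipid outcomes and all week 6 comparisons as exploratory. Report them as between-arm differences with 95% confidence intervals, with no claim of superiority.

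A fixed testing order for the secondary outcomes is optional in this pilot. It is needed only if a claim on a secondary outcome is wanted. In that case, order the section 2.1 outcomes at week 12, test them only after the primary lipid is significant, and stop at the first non-significant result.

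The cost is wording in two sections, with no new data or participants. The downside is that a significant secondary result can no longer be reported as showing that one diet is more effective.
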